## 1 Protocol Summary

Study Title	Prostatic Urethral Lift in Subjects with Acute Urinary Retention Study (PULSAR)
Study Objectives	Assess feasibility and safety of the Prostatic Urethra Lift (PUL) procedure in patients with acute urinary retention secondary to BPH. Research methodology will also be evaluated for larger, randomised study.
Study Design	Multi-centre, prospective evaluation of PUL and retrospective review of invasive surgery as potential comparator.
Sample Size	Up to 55 subjects treated with PUL. Retrospective chart review will include BPH patients that presented with AR and went on to de novo invasive surgery from June 1, 2015 to December 31, 2015.
Subject Population	Males over the age of 50 diagnosed with symptomatic benign prostatic hyperplasia (BPH) and ongoing acute urinary retention after failed TWOC.
Number of Centres (Sites)	Up to six centres in the United Kingdom.
Clinical Indication	The UroLift System is indicated for the treatment of symptoms due to urinary outflow obstruction secondary to benign prostatic hyperplasia (BPH) in men 50 years of age or older.
Primary Study Assessment	Successful post-procedure voiding trial without catheter (2-4 days).
Safety Assessment	Rate of serious adverse events (SAEs) related to BPH intervention through 3 months.
Additional Assessments	1. Need for further clean intermittent self-catheterisation (CISC) 2. Urinary symptoms, post void residual (PVR) and peak flow rate over follow-up 3. Subjects free from urinary retention through 1 month, 6 weeks, 3, 6 and 12 months 4. Subjects free from alternative surgical procedure for BPH through 12 months 5. Duration of catheter prior to treatment and in follow-up between prospective (PUL) and retrospective (TURP/HoLEP) 6. Rate of AEs in prospective PUL and retrospective TURP/HoLEP 7. Assess enrolment rate, willingness of patients to enrol, inclusion criteria, and appropriateness of endpoint
Follow-up Evaluations	Post-procedure, 6 weeks, 3 months, 6 months (remote), 12 months
Anticipated Study Duration	
First patient in (FPI)	15-April-2018
Last patient in (LPI)	31-December-2018
Endpoint analysis	28-February-2019
Study close	01-April-2020

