## 7 Study Design

---

The study is a multi-centre, consecutive, prospective feasibility study of the UroLift System in acute urinary retention (AR) patients. A retrospective dataset (patients treated from June 1, 2015 to December 31, 2015) of patients meeting similar criteria that underwent an invasive procedure to treat AR will be analysed against UroLift data. A maximum of 55 subjects undergoing UroLift will be enroled in up to six study centres in Great Britain. This feasibility study is the first to assess patients undergoing PUL with AR and will determine if a larger, quantitative study should be conducted with optimal methodology. By evaluating results pertaining to study design, primary study assessment, conduct of trial, site performance, subject compliance, and inclusion criteria specifically, a robust safety and effectiveness study can follow.

Clinical improvements will be assessed at post-procedure, 6 weeks, and months 3, 6, and 12 post-index procedure.

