## 9 Withdrawal Criteria

Subjects who have signed an informed consent form may be withdrawn from this study if they become unwilling or unable to comply with follow-up requirements, if they withdraw their consent, or if the investigator determines the subject should no longer continue in the study. Regardless of the

reason for withdrawal, data available for the subject at the time of withdrawal, including the reason for withdrawal, will be collected and entered in EDC. All practical efforts will be made to obtain the final AR status, retreatment status, and IPSS information.

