## 10.9 Interim Visits

Testing or procedures performed for adverse events associated with BPH or LUTS should be recorded and entered into eCRFs throughout the duration of subject follow-up even if outside protocol visit windows.

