## 10.10 Surgical Intervention

The following information will be collected in association with secondary interventions:

- Adverse Event leading to the intervention (Unless urinary retention- **See Section 14.3**)
- Date of procedure
- Type(s) of procedure(s) performed
- Pre-procedure diagnosis for undergoing procedure
- Complications (as Adverse Events)
- Count of UroLift implant removal(s) and placements, if applicable
- Catheterisation use

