### 10.10.1 Alternative Surgical Intervention

A subject with recurring urinary retention requiring catheter or other LUTS may require alternative surgical intervention (HoLEP, TURP, PVP, etc). The subject will remain in study through 12 months with the following abbreviated requirements:

- 1) Upon the surgery scheduling, study visits will no longer be required with the exception of the 12 month visit.
  - a. If subject is on catheter during the final visit (12 month) the urinalysis and urinary symptoms will not be required. Ongoing adverse events and catheterizations will be required. Refer to **Table 7**, Schedule of Procedures.
- 2) Between reintervention and 12 month visit, only urological serious adverse events (SAE) should be reported.

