## 16.6 Additional Assessments

---

Continuous measures will be summarised by visit. Summary statistics will include the available sample size, mean and standard deviation. Changes from baseline to each follow-up visit will also be calculated and the summary statistics will include the number of patients with change score available, mean, median, standard deviation, and confidence intervals (CI). These assessments will be calculated for both the ITT and PP analysis populations.

The Kaplan-Meier method will be used to calculate freedom from alternative secondary surgery over time and freedom from medical treatment, from the time of the PUL procedure for the ITT and PP populations. Subjects that do not have an alternative procedure will be censored at their last recorded follow-up visit. The probability of freedom from urinary retention will be analysed in a similar manner for the safety population. Time without catheter will be analysed using the Kaplan-Meier method in the ITT and PP populations.

Adverse events will be summarised by overall adverse events (AEs), severe AEs (grade 3 or higher on CTCAE scale), AEs related to device and/or procedure, serious adverse events (SAEs) and SAEs related to device and/or procedure. Adverse events will be coded using MedDRA and CTCAE v4.0 severity grades and will be presented by System Organ Class (SOC) and preferred term. Adverse events will be summarised for the safety population.

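### Section 16.6 censors men without surgery at their last visit but sets no matching cut-off for surgeries, so the 12-month surgery rate can be biased upward if later surgeries are counted

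*Combined protocol and SAP*

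**What the plan says.** The outcome is listed in the Protocol Summary (additional assessment 4) as "Subjects free from alternative surgical procedure for BPH through 12 months". Section 16.6 gives the method: "The Kaplan-Meier method will be used to calculate freedom from alternative secondary surgery over time and freedom from medical treatment", counted from the PUL procedure in the ITT and PP populations. The censoring rule is: "Subjects that do not have an alternative procedure will be censored at their last recorded follow-up visit". Freedom from urinary retention is to be handled in a similar manner. Section 16.6 does not say how the event is dated, or whether a surgery after a man's last attended visit counts.

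Four data-collection provisions bear on this:

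- Section 10.10: "The following information will be collected in association with secondary interventions". The list that follows includes the date of the procedure and ties nothing to a study visit.
- Section 10.9: tests or procedures for BPH or LUTS adverse events "should be recorded and entered into eCRFs throughout the duration of subject follow-up even if outside protocol visit windows".
- Section 10.10.1: "Upon the surgery scheduling, study visits will no longer be required with the exception of the 12 month visit".
- Section 9, on men who withdraw: "All practical efforts will be made to obtain the final AR status, retreatment status, and IPSS information".

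Section 16.4 plans no imputation. Section 7 sets the size: "A maximum of 55 subjects undergoing UroLift will be enroled in up to six study centres in Great Britain". No rate of surgery or of missed visits is given.

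**The concern.** Kaplan-Meier needs a man's time at risk to be settled without reference to whether he later has the event. A rule that ends follow-up at the last visit for men without surgery, but lets a surgery count on its own date, breaks this for anyone who misses month 12. Take two men last seen at 6 months. One is later found to have had surgery at day 240, so he stays in the risk set until day 240 and is an event. The other is confirmed free of surgery at an exit contact, yet on a literal reading he leaves the risk set at about day 182.

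The visit waiver in Section 10.10.1 adds to this. A man scheduled for surgery has no required visit before month 12. If operated on, he has a dated event. If never operated on and absent at month 12, his event-free time stops at a visit that may be months earlier.

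The 12-month figure is a named outcome that will inform a later controlled study. Section 16.6 also compares retreatment by time to event with the retrospective surgical arm. That arm has chart contacts instead of scheduled visits, and no censoring rule is stated for it.

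**Working it through.** The plan states no figure for this outcome, so there is nothing to reproduce. The check asks how large the effect could be.

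**Inputs.** From the documents: at most 55 men (Section 7), a 12-month horizon (Protocol Summary), and late contacts at 6 and 12 months (Sections 10.7 and 10.8). Assumed: a true 12-month surgery rate p of 25%; a share d of men who miss month 12; a share q of those men's later surgeries that is still found.

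**Closed form** (constant hazard, absent men last seen at 6 months). Survival to 6 months is √(1 − p) = √0.75 = 0.8660. The true conditional event rate from month 6 to 12 is u = 1 − 0.8660 = 0.1340. Under the asymmetric rule, the men followed after 6 months are the attenders (1 − d) plus only those absent men whose surgery is found (d·q·u). The events among them are u(1 − d + d·q). The conditional rate becomes

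u* = u(1 − d + d·q) / (1 − d + d·q·u),

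and the reported 12-month rate is 1 − 0.8660 × (1 − u*).

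- d = 10%, q = 1: u* = 0.1340 / 0.9134 = 0.1467; reported 26.1%.
- d = 20%, q = 1: u* = 0.1340 / 0.8268 = 0.1620; reported 27.4%.
- d = 10%, q = 0.5: u* = 0.1404; reported 25.5%.
- d = 20%, q = 0.5: u* = 0.1482; reported 26.2%.
- d = 0, or q = 0 with loss unrelated to risk: reported 25.0%, no bias.

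**Sensitivity to timing** (simulation, N = 55, true 25%). Late timing draws surgery dates from a triangular distribution over days 60 to 360 with mode 220, and last sees absent men at 3 or 6 months in equal parts. Uniform timing spreads dates evenly over the year, with last contact at 6 months.

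| Setting | 10% miss month 12 | 20% miss month 12 |
|---|---|---|
| Late timing, all surgeries found | 26.9% | 28.9% |
| Late timing, half found | 25.9% | 26.9% |
| Uniform timing, all found | 26.2% | 27.6% |
| Uniform timing, half found | 25.7% | 26.4% |
| One cut-off for events and event-free time | 25.0–25.1% | 25.0–25.1% |

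Across these settings the excess is about 0.5 to 2 points at 10% missed and about 1.5 to 4 points at 20% missed.

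**Sampling error.** √(0.25 × 0.75 / 55) = 0.058, or about 6 points.

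**Opposite direction.** Suppose men who miss month 12 have three times the hazard after 6 months and none of their later surgeries is found. Survival over months 6 to 12 is then 0.8660 for attenders and 0.8660³ for absent men. Kaplan-Meier reports 25.0%. The true rate is 1 − [(1 − d) × 0.75 + d × 0.75²], which is 26.9% at d = 10% and 28.75% at d = 20%. The estimate is then too low.

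**The case against.** The strongest reply is that half of the supposed rule is not in the analysis section. Section 16.6 fixes only when men without surgery are censored. That later surgeries count is inferred from data-collection text, and that text has limits. Section 10.9 covers procedures for adverse events during follow-up, and Section 14.3 says recurrent retention is not an adverse event. Section 10.10 lists what is collected, not how absent men are traced. If surgeries after the last visit are not counted and loss is unrelated to risk, there is no bias. The word visit can also be read broadly: the schedule of procedures has a phone visit and a study-exit column, so an exit contact might qualify. Censoring at last follow-up is a common convention, and Sections 10.12 and 16.4 plan for retention.

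Much of this stands, and it rules out two stronger readings. A reader might infer that the rate is overstated as the plan is written. The documents do not support that, because counting later surgery is allowed but not stated, and size and direction depend on who is missed and what is found. A reader might also infer that men who miss late visits add no event-free time. They add it up to their last visit; only the later time is lost. Nor do the documents establish that surgery clusters after the 6-month call. The 30-week wait in Section 6 runs from counselling, and Section 10.1 includes surgical waiting lists among the recruitment sources.

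What does not stand is that the sentence can be left alone. It applies only to men without an alternative procedure, and nothing removes a dated surgery that follows the last visit. For men whose visits were waived because surgery was scheduled, counting that surgery is the natural reading.

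**Conclusion.** The point holds conditionally. Section 16.6 sets a censoring date for men without surgery and no matching limit on events. If later surgeries are counted, the 12-month surgery rate is biased upward by the amounts shown above, on assumed rates of surgery, missed visits and tracing. At 55 men the excess is smaller than the sampling SD in every setting tried. It disappears with complete 12-month visits and can reverse when absent men's surgeries go unrecorded.

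The consequence is limited. This is a descriptive additional assessment, Section 16.7 sets no success criterion, and Section 16.6 says the comparison with the retrospective arm is not powered. It is a cheap improvement of minor severity.

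**What to change.** In Section 16.6, replace the last recorded follow-up visit with the last date on which surgical (or, for that outcome, retention) status was confirmed by visit, telephone, exit contact or record check. Date the event by the procedure date, and apply the same cut-off to events and to event-free time.

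Record the status date at study exit. Seek it for every man who misses month 12, whether or not a surgery is already known. Where status after the last visit was not sought on that basis, use neither events nor event-free time beyond that visit, with one exception: do not discard the dated surgeries of men whose visits were waived under Section 10.10.1. Dropping those would censor men because they were about to have the event. Instead, seek status on the same basis for men who were scheduled and not operated on.

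The cost is a revised sentence or two in Section 16.6, one date field, and a status check for the men who miss month 12. Section 9 already asks for this effort for men who withdraw.

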## 6.4 Other Assessments

---

Several other outcomes will be analyzed during the 12 month follow-up to understand post-TWOC durability:

- Catheter free rate and days free from catheter at 1 month and throughout follow-up
- Number of subjects who failed initial attempt but are able to void in subsequent TWOC
- Need for further clean intermittent self-catheterisation (CISC)
- Urinary symptoms peak flow rate, post void residual (PVR) volume
- Subjects free from alternative surgical procedure for BPH
- Duration of pre-index procedure catheter and its impact on durability
- Rate of adverse events
- The prospective arm will be compared to the available data collected in the retrospective surgical arm

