### 10.3.4 Post Procedure Instructions

After creating an unobstructed anterior channel, continue with cystoscopy to verify implants are not present in the bladder, or extending into the bladder vesical. Interrogate the bladder neck for protruding implants. If a protruding or exposed implant is present, it should be removed.

A urinary catheter will be placed prophylactically after the Investigator completes the UroLift procedure, and subject provided instructions on its proper maintenance. The subject should remain on

alpha blockers per the site's standard of care. Initiation and cessation should be documented on the concomitant medication log. A post-procedure follow-up visit to perform Trial without Catheter will be scheduled for 3 days ( $\pm 1$  day) after index procedure.

The Investigator or designee will record the following procedural data:

- Device: number of UroLift devices used, location of implantation, lot number, performance
- Cystoscopy findings, including confirmation of inclusion criteria, stones, and other notable pathology
- Time: subject enters and leaves procedure room, first/last UroLift device, catheter placement
- Anaesthesia/sedation: duration, type, and delivery of procedural medications
- Clinical staff required during the procedure
- Complications/adverse events
- Venue type (clinic, outpatient, inpatient, etc.)
- Time to discharge or release from treatment facility
- Urinary catheter placement, type and timing (length)
- Medications used
- Post-operative interventions (if any)

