#### 10.4 Post-Procedure Trial Without Catheter (TWOC)

The subject will return to clinic **3 days ( $\pm 1$  day)** after Index procedure for the primary study assessment screening of bladder function without catheter. TWOC will be considered successful if the spontaneous void is  $\geq 100$  mL with PVR  $< 300$  mL. If subject fails the initial TWOC, at least one additional TWOC will be performed per standard of care. All catheterisations will be recorded on the eCRF.

The following evaluations will be performed in office **3 days ( $\pm 1$  day)** after index procedure in conjunction with the TWOC:

- Relevant Concomitant medications: BPH/LUTS; Sexual Function; GU; Prostate Cancer
- Freestanding uroflow and post void residual (PVR)
- Catheterisation review
- Adverse Event review; Intervention review

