### **Primary Study Assessment:**

TWOC is a binary measure of success. The percent of subjects who have a successful TWOC at the 3 day post procedure visit will be presented. Secondary assessments will include the catheter free rate at 1 month along with time without catheter. This primary study assessment will be calculated for both the ITT and the PP analysis populations.

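### Section 6.4 lists days free from catheter, but the only analysis named for catheter-free time is an undefined Kaplan-Meier curve, which cannot total the days when men recover late and relapse

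*Combined protocol and SAP*

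**What the plan says.** Section 6.4, headed Other Assessments, lists: "Catheter free rate and days free from catheter at 1 month and throughout follow-up". Section 16.5 raises catheter-free time to a secondary assessment in slightly different words: "Secondary assessments will include the catheter free rate at 1 month along with time without catheter". Section 16.6 then names the method: "Time without catheter will be analysed using the Kaplan-Meier method in the ITT and PP populations". None of these sections says when the clock starts, what the event is, or what happens when a man goes back on a catheter and comes off again.

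The rest of the protocol makes catheter status reversible:
- Section 10.3.4: "A urinary catheter will be placed prophylactically after the Investigator completes the UroLift procedure". So every man starts follow-up on a catheter.
- Section 10.4: "If subject fails the initial TWOC, at least one additional TWOC will be performed per standard of care".
- Section 6.4 counts late recoverers as an outcome: "Number of subjects who failed initial attempt but are able to void in subsequent TWOC".
- Section 6.4 also tracks further clean intermittent self-catheterisation (CISC), and section 10.10.1 foresees recurrent retention that needs a catheter.

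On data, section 10.4 says: "All catheterisations will be recorded on the eCRF". Table 7 schedules a catheterisation review at every visit.

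**The concern.** A number of days free from catheter is a cumulative quantity. Each man's catheter-free spells have to be added and his days on a catheter left out. A Kaplan-Meier curve describes the time to one event per man. If men come off, go back on and come off again, the curve and the day total are different quantities, and the plan names an analysis only for the first.

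Section 6.4 says its outcomes are there to show durability after the TWOC, and section 6.1 says the study will help settle the endpoint for a larger study. A figure for catheter-free time that turns on an event definition chosen after the data are seen would be a weak basis for that. The protocol summary (additional assessment 5) also promises a comparison of catheter duration during follow-up with the surgical cohort. Section 16 specifies no per-man total for that either.

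**Working it through.** The plan gives no figure for catheter-free days, so there is nothing to reproduce. The check compares candidate Kaplan-Meier definitions with the true day count.

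**Inputs.** From the documents: catheter in place after the procedure (10.3.4), first TWOC at day 3 (10.4), repeat TWOC after failure (10.4). Assumed for illustration: later success on day 14, a temporary recatheterisation on days 60 to 67, a permanent one from day 60, and a horizon of 365 days.

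**Single men.** Three definitions are compared:
- D1: clock starts at the day-3 removal for everyone; event is first recatheterisation.
- D2: clock starts at the procedure; event is first successful TWOC; days after the event are credited.
- D3: clock starts at each man's first successful TWOC; event is first recatheterisation.

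| Course | True catheter-free days | D1 | D2 | D3 |
|---|---|---|---|---|
| A: fails day 3, voids from day 14 | 365 − 14 = 351 | 0 | 351 | 351 |
| B: passes day 3, catheter on days 60–67 only | (60 − 3) + (365 − 67) = 355 | 57 | 362 | 57 |
| C: passes day 3, catheter from day 60 for good | 60 − 3 = 57 | 57 | 362 | 57 |
| D: fails day 3, voids from day 14, catheter on days 60–67 | (60 − 14) + (365 − 67) = 344 | 0 | 351 | 46 |

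D1 is right only for C, and D2 only for A. D3 is right for A and C, who each have one catheter-free spell, but it has no starting point for a man who never passes a TWOC. Courses B and D, with two spells, are wrong under all three.

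**Cohort mean without relapse.** Let f be the day-3 failure rate, s the later success rate and H the horizon.
- True mean = (1 − f)(H − 3) + f·s·(H − 14).
- D1, area under the curve = (1 − f)(H − 3).
- D2, area above the curve = (1 − f)(H − 3) + f·s·(H − 14), which equals the true mean.

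At H = 365, f = 0.30 and s = 0.295 (the background repeat-TWOC success rate in section 6, from men not treated with PUL):
- D1 = 0.70 × 362 = 253.4.
- True mean = 253.4 + 0.30 × 0.295 × 351 = 253.4 + 31.1 = 284.5.
- D1 misses 31.1 / 284.5 = 11%. D2 misses nothing.

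At s = 0.90 the added term is 0.30 × 0.90 × 351 = 94.8. The true mean is 348.2 and D1 misses 27%. Over f from 0.10 to 0.50 and s from 0.295 to 0.90, D1 misses 3% to 47% at 365 days and 2% to 35% at 30 days. These percentages apply only to D1, and f, s and day 14 are assumed.

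**Cohort mean with relapse.** D2 overstates the mean by the average number of recatheterised days per man. That is 7 days for a man on course B (362 − 355) and 305 for a man on course C (362 − 57). The documents give no relapse rate, so no cohort figure follows.

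**The case against.** The strongest reply is that the plan is under-specified rather than wrong. If no man relapses, a Kaplan-Meier curve of time from the procedure to first successful TWOC gives the exact mean, as shown for D2. Any loss from missing late recoverers therefore comes from choosing first recatheterisation as the event with a day-3 clock, and section 16.6 does not state that choice. This stands. A reader might infer that Kaplan-Meier will understate catheter-free days by some fixed percentage here; the documents do not support that.

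A second reply is that days free from catheter and time without catheter may be two separate displays, with the day count covered by the general rule "Continuous measures will be summarised by visit". No sentence equates the two terms, so this reading is possible. But the general rule does not name catheter days, a by-visit summary is not a running total, and the only method attached to catheter-free time is Kaplan-Meier.

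Third, late recoverers do not disappear. They are counted in section 6.4, and section 10.11 uses the duration of indwelling-catheter dependence when treatment failure is judged. This also stands: the days are missing from the specified analysis, not from the database.

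Fourth, section 16.7 sets no formal success criterion, so no decision rule depends on this curve. That limits the consequence. Nor do the documents rank catheter-free time as the main durability measure; it is one of several in section 6.4.

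**Conclusion.** The point holds as a mismatch between a listed outcome and its named analysis, and it should be corrected. Kaplan-Meier, with no origin, event or repeat-episode rule, does not deliver the day total. With a clock common to all men, first recatheterisation drops late recoverers, and first successful TWOC never subtracts later catheter days. A clock that starts at each man's own first success works only for men with a single catheter-free spell. No single-event definition totals the days in a cohort where men both recover late and relapse, with catheter-free time resuming afterwards.

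The individual examples (0 of 351 days, 57 of 355) depend on a first-recatheterisation event with the clock at day 3. The cohort error could be near zero or large, in either direction, depending on the event chosen and on failure and relapse rates that the documents do not give. The documents do not support a single percentage, or the claim that Kaplan-Meier fails under every pattern of outcomes. As this is a feasibility study without success criteria, the harm is to how the durability result is read and carried into a larger trial.

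**What to change.** In section 16.6:
- **Add a per-man total.** Count catheter-free days from the catheter dates on the eCRF, adding all catheter-free spells, to day 30 and to the 12-month visit. Report mean, median and a bootstrap 95% CI (resampling men) for ITT and PP.
- **Apply the existing censoring rule.** The opening of section 16 censors effectiveness the day after surgical retreatment, including a second PUL. The day count should follow it.
- **Handle incomplete follow-up.** Section 16.4 plans no imputation, and the ±30-day window allows a 12-month visit before day 365. Either integrate the daily proportion catheter-free among men still under observation, or report days free over days observed.
- **State how CISC days are classified.**
- **Keep Kaplan-Meier as a supplementary curve** for a defined event: time from first successful TWOC to first recatheterisation.

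The cost is SAP wording and a little more programming. No new data are needed if the form holds insertion and removal dates for each catheterisation; this should be confirmed. The downside is that the total rests on an assumption about censored time. Men on a catheter may be more likely to have further surgery, so dropping them at retreatment could make the daily proportion look too favourable. The report should say so and give the number censored for this reason.
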